	
2) Tissue will be removed as part of the standard neurosurgical procedure. Normal tissue obtained from inevitable resection during the course of surgery. There will be no deviation from normal surgical practice to acquire tissue samples.
 
3) Image recordings of sample tissue using cCeLL – Ex vivo are taken and the obtained data is stored (CC).
 
4) cCeLL – Ex vivo image data of the collected samples is sent to the central core.
 
5) The result of frozen section analysis (FS) will be collected from the pathology department of each site.
 
6) The result of permanent section analysis (PS) of corresponding paraffin-embedded tissue section (PS) will be collected from the pathology department of each site. PS will serve as a reference standard to the analysis result of CC and FS.
 
7) An interpreting pathologist will analyze given images (CC-H) and is not allowed to review the reference standards (PS) until all interpretations have been completed.
 
8) The cCeLL – Ex vivo image data will be anonymized such that only the unique reference numbers will be displayed in the images provided, and participant information including participant enrollment number and surgery information will be removed.
 
9) The types of the images obtained from this procedure are as follows:
 
cCeLL – Ex vivo will capture image data of a resected tissue, prior to frozen sectioning (FS) and permanent sectioning (PS). The biopsied samples can be used to evaluate the presence of tumors, and the tumor types.
 

Method of analysis	Image data	Reference standard	Result of analysis by a pathologist	

cCeLL – Ex vivo	CC	PS	CC-H	

Permanent section	PS	PS		

Frozen Section	FS	PS		

 
CC : Analysis of images obtained by cCeLL FS : Frozen section analysis PS : Permanent section analysis H : Pathologist
 
10) Data will be analyzed by a statistician. Sensitivity and specificity will be calculated as follows:
	Method of analysis	Image data	Reference standard	Result of analysis by a pathologist	cCeLL – Ex vivo	CC	PS	CC-H	Permanent section	PS	PS		Frozen Section	FS	PS	
Method of analysis	Image data	Reference standard	Result of analysis by a pathologist														
cCeLL – Ex vivo	CC	PS	CC-H														

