Analysis Methods	
Primary Endpoints
 
Comparison of the sensitivity/specificity of cCeLL-Ex vivo reading results, and the sensitivity/specificity of the frozen section reading results in one pathological inquiry for brain tumor tissue
 

• Sensitivity of cCeLL-Ex vivo reading result in 1 patient in pathological inquiry for brain tumor tissue: Probability that PS is positive if CC-H positive

• Specificity of cCeLL-Ex vivo reading result in 1 patient in pathological inquiry for brain tumor tissue: Probability that PS is negative if CC-H is negative

• Sensitivity of frozen section reading results for brain tumor tissue: Probability that FS is positive if PS is positive

• Specificity of frozen section reading results from brain tumor tissue: Probability that PS is negative if FS is negative

 
The ratio of the clinical sensitivity/specificity of a cCeLL Ex-vivo image and the sensitivity/specificity of the frozen section image of 1 patient in the pathological inquiry for the total reading results is presented, respectively. To identify a 95 % bilateral confidence interval for the difference between cCeLL- Ex vivo and the frozen section sensitivity/specificity.
 
The statistical significance of the difference between cCeLL-Ex vivo and the frozen section sensitivity/specificity ratio is tested by the McNemar test.
 
Secondary Endpoints
 

1. Comparison of cCeLL-Ex vivo imaging and reading time with frozen section reading time

i. The cCeLL-Ex vivo imaging time is measured and recorded in minutes from the time the fluorescent dye is applied to the specimen for image acquisition

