	
ii. The cCeLL-Ex vivo reading time by the pathologist is measured and recorded in minutes from the time of capturing the cCeLL-Ex vivo image of each brain tumor to the time of the final reading.
 
iii. The imaging and reading time for frozen section is measured in minutes from the time of resecting the specimen undergoing frozen section in the operating room to the time when the pathology department of each institution obtains a frozen section image and reports the findings.
 
iv. Format: _____ Hours _____ Minutes
 
2. Comparison of cCeLL accuracy of evaluating the tumor types via Ex-vivo imaging with the accuracy using frozen section
 

i. Evaluation of tumor types via cCeLL-Ex vivo images by 1 pathologist : Agreement between the result of CC-H and the result of PS

ii. Evaluation of tumor types via frozen section: Agreement between the result of FS and the result of PS

 
3. cCeLL – Time and number of images required to diagnose Ex vivo imaging
 

i. The number of images required for the pathologist to read the brain tumor cCeLL – Ex vivo image will be measured and averaged.

ii. cCeLL – Ex vivo reading time uses that of secondary endpoint 1.

iii. *Average number of images required for cCeLL – Ex vivo image reading of 1 brain tumor specimen: _____

 
4. Non-diagnostic image
 

i. The total number of cCeLL Ex-vivo images among the images confirmed in the vivo reading, and the proportion of the number of images that cannot be read are stated as a percentage (%).

ii. The number of images that cannot be read is recorded when the reader reads it.

 
5. AUC value
 

i. Based on the results of each endpoint, the sensitivity and false positive rate (1-specificity) are used to draw the ROC (Receiver Operating Characteristic) Curve to evaluate the performance of the diagnosis to distinguish between positive and negative, and the accuracy of the diagnosis is evaluated through the AUC (Area Under the Curve) value obtained from the area below the ROC curve.

--	--

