### **8.2 Secondary Endpoints**

1. Comparison of time taken in tissue scanning, visualization, and interpretation using cCeLL – Ex vivo to time taken in frozen section analysis.
2. Accuracy in determining the tumor type
3. Required image counts for adequate analysis and diagnosis using cCeLL – Ex vivo
4. Non-diagnostic Image
5. AUC value

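### The cCeLL reading time starts at image capture, not when the pathologist opens the image, so it includes any study-only handling lag, and secondary endpoint 3 inherits it

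*Combined protocol and SAP*

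**What the plan says.** The timing definitions are in the Synopsis, Analysis Methods, under the secondary endpoints.

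- **Endpoint 1(i), imaging time:** "The cCeLL-Ex vivo imaging time is measured and recorded in minutes from the time the fluorescent dye is applied to the specimen". No stop event is spelled out.
- **Endpoint 1(ii), reading time by the pathologist:** "from the time of capturing the cCeLL-Ex vivo image of each brain tumor to the time of the final reading".
- **Endpoint 1(iii), frozen section:** one clock from resection in the operating room to the pathology department's report.
- **Endpoint 3:** headed "Time and number of images required to diagnose Ex vivo imaging", with the time taken from endpoint 1: "cCeLL – Ex vivo reading time uses that of secondary endpoint 1".

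The endpoint lists (Synopsis, Study Endpoints; section 8.2) give endpoint 3 without a time component: "Required image counts for adequate analysis and diagnosis using cCeLL".

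On workflow, Study Procedure item 4 in the Synopsis says "cCeLL – Ex vivo image data of the collected samples is sent to the central core", and section 6.2 item 5 repeats this. Synopsis item 8 and section 6.2 item 9 have participant and surgery information removed from the images supplied for reading. Section 6.6 promises start and stop times for each test in general terms.

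**The concern.** A quantity labelled as the pathologist's reading time should start when the pathologist starts reading. This one starts when the image is captured, before the reader has it. Any time spent on transfer, de-identification or waiting for the reader is counted as time required to diagnose.

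Speed is the stated rationale for the device. A reading time that contains study logistics cannot show how long interpretation takes, and it may differ between sites for reasons unrelated to the reader or the device. The same value also feeds endpoint 1, the comparison with frozen section, where a lag that exists only because of the study would count against cCeLL.

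This is separate from the different start points of the cCeLL and frozen-section clocks (dye application versus resection). Aligning those would leave the lag inside the endpoint 3 reading time.

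**Working it through.** The plan gives no expected reading time, transfer time or waiting time, so there is no figure to reproduce. The check sets the definitions against the workflow.

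**Step 1: what lies between capture and final reading.**

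| Event | Source | Inside the 1(ii) clock? |
|---|---|---|
| Image captured | Synopsis 1(ii) | Start |
| Image data sent to the central core | Synopsis, Study Procedure item 4; section 6.2 item 5 | Yes, if done before reading |
| Identifying information removed | Synopsis item 8; section 6.2 item 9 | Yes |
| Waiting for the reader | Not described | Yes, if any |
| Pathologist opens the images | No timestamp named | Yes, unmarked |
| Final reading | Synopsis 1(ii) | Stop |

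**Step 2: is the lag removed or bounded anywhere?** No section subtracts it. Section 6.6 is generic and names no reading-start time. Section 7.1 bases clinical decisions on standard-of-care images, so nothing obliges anyone to read the cCeLL image during surgery.

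**Step 3: who reads, and where?** The Synopsis (Study Endpoints) and section 8.1 refer to a single pathologist, in a study with four sites in two countries. Section 6.7 says the blinded assessments come from the site pathologist. The central-core step does not say whether reading takes place there, or only after transfer. The text therefore allows anything from a prompt local read to a deferred central one.

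**Step 4: what the clock returns.**

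Recorded reading time = r + L, where r is active reading and L is the time from capture to opening. The share that is not reading is L / (r + L).

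Both values are assumptions. With r = 5 minutes:

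| L (min) | Recorded (min) | Share not reading |
|---|---|---|
| 0 | 5 + 0 = 5 | 0% |
| 10 | 5 + 10 = 15 | 10/15 = 67% |
| 60 | 5 + 60 = 65 | 60/65 = 92% |
| 1,440 (one day) | 5 + 1,440 = 1,445 | 1,440/1,445 = 99.7% |

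The recorded value equals r only when L = 0. The table shows how sensitive the measure is; it does not estimate what will happen in this study.

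**The case against.** The case on the other side has several parts.

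- **A read apart from surgery is not stated.** A reader might infer deferred batch reading from the rule that the pathologist "is not allowed to review the reference standards (PS) until all interpretations have been completed". That is a blinding rule about access to the permanent section. It fits case-by-case reading equally well, and the matching step in section 6.2 (item 8) omits the phrase. With section 6.7 naming the site pathologist, a prompt local read with a lag near zero is possible. This stands.
- **The clock does not measure transfer and queue time alone.** A reader might infer that it does, but interpretation is always part of the interval, and the documents do not show that lag dominates it. This stands.
- **The hours-and-minutes recording format is not a defect.** A reader might infer that it cannot hold a later-day read. If the blanks hold a duration, a long one fits.
- **The protocol's 40-minute average is not a yardstick for reading time.** It describes the whole frozen-section process. Saying that an assumed 60-minute lag exceeds it adds nothing about this study.
- **Endpoint 3 is listed as image counts only, and the secondary endpoints are descriptive** (section 8.3.1, closing statement). This stands and limits the consequence.
- **Capture-to-report turnaround is a legitimate measure.** It is, for an elapsed-time comparison. Dropping all capture-to-opening time from endpoint 1 would favour cCeLL, because the frozen-section clock includes transport and handling and some delivery delay would also occur in routine use. This stands and shapes the fix.

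None of this changes the fact that the definition starts before reading starts and that no other recorded time allows a correction.

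**Conclusion.** The point holds as a defect of definition. As written, endpoint 1(ii) yields interpretation plus whatever time passes before the image is opened, and endpoint 3(ii) presents that as time to diagnose. It is a true reading time only if images are opened at capture, which the protocol neither requires nor rules out.

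The size is unknown. It depends on where and when images are read, on which the Synopsis and sections 6.2, 6.7 and 8.1 do not give one consistent account. The documents do not support saying that the lag is large.

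The consequence is limited to descriptive secondary results: the time element of endpoint 3 and the cCeLL side of endpoint 1. Agreement, sensitivity, specificity and the 250-sample target are unaffected. It is still worth settling prospectively, because an opening time that was not recorded may not be recoverable.

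**What to change.** 1. Record in the eCRF the date and time at which the interpreting pathologist opens the first image of each specimen.
2. For endpoint 3, define reading time as that opening to the final reading.
3. Report the latency from capture to opening separately.
4. For endpoint 1, keep and report the full elapsed cCeLL time together with its components: imaging, latency and reading. Give the imaging clock in 1(i) an explicit stop at capture so that the components add up. This shows how much of any difference from frozen section is study logistics without tilting the comparison toward the device.
5. Reconcile the Synopsis (Study Procedure and Study Endpoints) with sections 6.2, 6.7 and 8.1 on where and when the images are read and by whom. Align the endpoint 3 wording in section 8.2 with the Analysis Methods on whether time is part of it.

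The cost is one extra timestamp per specimen and a few sentences of text. Opening-to-reading time describes active interpretation, not turnaround, which is why the elapsed time is kept for endpoint 1.

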### 3.2 Background

Cancer is a leading cause of death, accounting for nearly 1 out of 6 death worldwide (Ferlay et al., 2020; de Martel et al., 2020; WHO, 2020).

[figure not shown]
The existing workflow for intraoperative brain tumor diagnosis involves tissue biopsy, processing, analysis and confirmation by a pathologist using frozen section, and relaying the result back to the surgeon. The current intraoperative diagnosis based on frozen section analysis is time-, resource-, and labor-intensive. The process takes over 40 minutes on average but may

take longer if biopsied specimen is insufficient or requires repeated analysis. Thereby the development of an efficient device that allows intraoperative real-time diagnosis is enforced.

Confocal Laser Endomicroscopy is a promising diagnostic tool to replace current standard ‘frozen section analysis’ by allowing intraoperative real-time high-resolution visualization of tissue of interest. Confocal Fluorescence Endomicroscopy follows the general principles of fluorescence, which is the characteristic of fluorescence-stained specimen (‘tissue’) that absorb light of short-wavelength and emits light of long-wavelength. This medical device visualizes the intensity of light emitted from a specimen which varies according to the specimen’s degree of light absorbance (White et al., 1987; Amos and White, 2003).

When the probe of the device, which contains optical fibers, is placed in contact with the specimen or close to within several hundred  $\mu\text{m}$  of the specimen, the optical signal generated from the main body gets transmitted to the specimen through the probe and then absorbed by the specimen. The specimen then gets activated and emits fluorescent light, and this fluorescent light returns to the main body of the device through the optical fibers of the probe. The mechanism behind optical fibers is that light incident at a specific angle proceeds to total reflection due to the inside and outside of the optical fibers each being made with differing densities and refractive indices. The optical signal which returned to the main body through the optical fibers is detected as an electronic signal by the photodetector in the main body. The electric signal is then converted to a digital signal by the converter inside the main body of the device, and the digital signal is then processed by the PC through its software and exported as an image onto the monitor.

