#### **4.4 Intended Use**

This investigational medical device is a diagnostic tool that aims to provide rapid and precise intraoperative assessment of biopsied neoplastic tissue specimen from a brain tumor. By enabling the fluorescence staining, visualizing, capturing and storing image data while in the operation room, standard time-consuming and labor-intensive preparation of specimen sectioning may not be necessary.

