## 6.2 Study Assessments and Procedures

There will be up to three (3) tissue sample types assessed for each participant: 1- center-of-tumor, 2- normal tissue (collected from inevitable standard resection), and 3- margin tissue. Depending on each participant's circumstance, the number of sample tissues harvested will differ from minimum of one to maximum of three. All tissue samples will be assessed with the investigative device and compared against frozen section analysis.

1. Samples will be collected from consented participants who have satisfied the eligibility criteria.
2. Tissues will be removed as part of the standard neurosurgical procedure. Normal tissues obtained from inevitable resection during the course of surgery.
3. Collected samples will be processed as follows:
  1. Wash the biopsied tissue with Phosphate Buffered Saline (PBS)
  2. Place the tissue on a glass slide
  3. Apply dye onto the tissue
  4. After 1 minute, wipe on gauze and then scan (i.e., cCeLL imaging) the tissue using Pixecton (probe) connected to cCeLL – Ex vivo
  5. Send the processed tissue to pathology to obtain images in the form for frozen sections analysis (FS)/permanent sections analysis (PS)
4. Image recordings of sample tissue using cCeLL – Ex vivo are taken and the obtained data is stored (CC).
5. cCeLL – Ex vivo image data of the collected samples is sent to the central core.
6. The result of frozen section analysis (FS) will be collected from the pathology department of each site.
7. The result of permanent section analysis (PS) of corresponding paraffin-embedded tissue section (PS) will be collected from the pathology department of each site. PS will serve as a reference standard to the analysis result of CC and FS.
8. An interpreting pathologist will analyze given images (CC) and is not allowed to review the reference standards (PS).
9. The cCeLL – Ex vivo image data will be de-identified such that only the unique reference numbers will be displayed in the images provided, and participant information including participant enrollment number and surgery information will be removed.
10. The types of the images obtained from this procedure are as follows:

cCeLL – Ex vivo will capture image data of a resected tissue, prior to frozen sectioning (FS) and permanent sectioning (PS). The sample is used to evaluate the presence or absence of tumors, and also to evaluate the tumor types.

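### Secondary endpoint 1 times cCeLL from dye application but frozen section from resection, with cCeLL handling possibly inside the frozen-section time, so the two times are not comparable

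*Combined protocol and SAP*

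**What the plan says.** The definitions are in the Synopsis, Analysis Methods, secondary endpoint 1.

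- cCeLL imaging: "The cCeLL-Ex vivo imaging time is measured and recorded in minutes from the time the fluorescent dye is applied to the specimen". The item gives no stop event.
- cCeLL reading: "from the time of capturing the cCeLL-Ex vivo image of each brain tumor to the time of the final reading".
- Frozen section: "from the time of resecting the specimen undergoing frozen section in the operating room to the time when the pathology department" has its image and reports.

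Section 6.2, item 3 gives the order of work on each sample: wash in PBS, place on a slide, apply dye, then "After 1 minute, wipe on gauze and then scan", and only then "Send the processed tissue to pathology to obtain images in the form for frozen sections analysis (FS)/permanent sections analysis (PS"). Item 9 of the Synopsis study procedure also places cCeLL imaging before frozen sectioning. Section 6.1 describes the samples as paired.

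Section 6.2, item 5 sends the images to a central core, and Section 6.7 has the site pathologist document the blinded reads. No section says when a read takes place. Section 6.6 promises start and stop times for each test but does not name the events. Secondary endpoint 3 reuses the reading time from endpoint 1. Section 8.3.1 limits all secondary endpoints to descriptive statistics.

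**The concern.** A time comparison can be interpreted only if both clocks start at the same event and neither is charged for the other's work. Here the start events differ, and on the written order of work the frozen-section clock keeps running while the tissue is prepared and scanned for cCeLL. Routine frozen section would not include those steps.

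Speed is central to the case for the device. Section 4.4 says it "aims to provide rapid and precise intraoperative assessment of biopsied neoplastic tissue specimen from a brain tumor", and Section 3.2 argues against frozen section on the ground that "The process takes over 40 minutes on average". This is also the first secondary endpoint. Because it is not tested, the reported difference is the whole result, and no later step would reveal the mismatch. If the extra times are not recorded prospectively, it may not be possible to remove the distortion afterwards.

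**Working it through.** The plan gives no expected time difference, so there is no figure to reproduce. The check is an account of which minutes fall in which clock.

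**Inputs from the documents.** Dye wait: 1 minute (Section 6.2). Average frozen-section process: over 40 minutes (Section 3.2). Samples to be collected: 358 (Section 5.4.1).

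**Symbols (durations not given in the documents).**
- w0 = resection to start of cCeLL handling
- w1 = wash and slide placement
- s = dye application to end of scan, including the 1-minute wait
- F = release to pathology until the frozen-section report, with transport and laboratory queue; release is taken at the end of the scan
- q = end of scan to read opened
- r = read opened to read closed
- o = minutes counted in both cCeLL imaging and reading, possible because reading starts at capture and imaging has no stated end

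**Step 1: times as the plan records them.**
- Frozen section = w0 + w1 + s + F
- cCeLL = s + q + r + o
- Difference (frozen section minus cCeLL) = w0 + w1 + F − q − r − o

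**Step 2: comparable times.** Both run from resection, waiting is kept in both, and the cCeLL handling is assumed to delay frozen section minute for minute.
- Frozen section = w0 + F
- cCeLL = w0 + w1 + s + q + r
- Difference = F − w1 − s − q − r

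**Step 3: shift (recorded minus comparable difference).**
- Shift = w0 + 2·w1 + s − o, where w0 + w1 comes from the different start, w1 + s from the handling inside the frozen-section clock, and −o from the overlap. The queue q cancels.
- No image exists before the dye wait ends, so o ≤ s − 1 and the shift is at least w0 + 2·w1 + 1, hence at least 1 minute toward cCeLL.
- A hold between end of scan and release adds its full length.

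**Step 4: size under assumed durations.**

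| Assumed case | Shift at o = 0 | Shift at maximum overlap |
|---|---|---|
| Low: w0 = 1, w1 = 1, s = 3 | 1 + 2 + 3 = 6 min | 6 − 2 = 4 min |
| High: w0 = 8, w1 = 2, s = 10 | 8 + 4 + 10 = 22 min | 22 − 9 = 13 min |

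Against 40 minutes these are 15% and 55% at o = 0, and 10% and 32.5% at maximum overlap. Since the stated average is over 40 minutes, the shares are upper limits for these cases.

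Example at o = 0: let both methods take 40 minutes on the comparable clocks. Recorded frozen section is 40 + w1 + s, that is 44 (low) or 52 (high). Recorded cCeLL is 40 − w0 − w1, that is 38 or 30. The plan would record gaps of 6 or 22 minutes where there is none.

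**Step 5: how far the result depends on the conditions in Step 2.**
- Keep frozen-section waiting but treat q as a study artefact: shift = w0 + 2·w1 + s − q − o. In the low case at o = 0 this is 6 − q, which is negative once q exceeds 6 minutes.
- Remove waiting from both methods, with f the frozen-section transport and queue: shift = w0 + 2·w1 + s + f − q − o. The sign is open.
- Handling runs entirely within a wait for pick-up that would have happened anyway: shift = w0 + w1 − o. With w0 = 1, w1 = 1, s = 10, o = 9 this is −7 minutes.

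**Step 6: the recorded difference itself.** From Step 1 it falls minute for minute as q grows. With w0 = o = 0, assumed values w1 = 5, F = 75, q = 0, r = 1 give 5 + 75 − 1 = +79 minutes. Values w1 = 0, F = 20, q = 1,440 (a read one day later), r = 10 give 20 − 1,440 − 10 = −1,430 minutes.

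**The case against.** The strongest objection is to any claim about direction. A reader might infer that the plan will record cCeLL as faster by at least 1 minute. The documents do not support that. The bound in Step 3 applies to a shift against one chosen comparison, not to the recorded difference, and Step 6 shows that the recorded difference has no fixed sign. The bound also assumes that handling lies wholly on the path to the frozen-section report, which no section states. Nor is the sign of the shift open only when waiting is removed from both methods: it is also open when the cCeLL queue alone is discounted. That may be a sensible choice, because Section 7.1 bases clinical decisions on standard-of-care images and nothing requires an intraoperative cCeLL read. These objections stand, and the point is limited accordingly.

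A second objection is that Section 8.2 defines the endpoint as scanning, visualization and interpretation, so a start at dye application fits its scope. That is fair for the cCeLL clock alone. It does not justify starting the comparator at resection.

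A third is that frozen section might use a different piece of tissue. Section 6.2 sends on the tissue that has just been processed, and the start events would differ in any case.

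Finally, the only documented component of the shift is 1 minute, which equals the recording unit, and Section 6.6 already plans to collect times. Both are true. The larger figures are illustrations, and Section 6.6 needs defined events before it can help.

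**Conclusion.** Wrong as written. Followed exactly, the definitions give a difference between two times that do not measure the same span of work. The different start and the handling inside the frozen-section time both shift that difference toward cCeLL. The shift is w0 + 2·w1 + s − o, and at least 1 minute, provided that waiting is kept in both methods and handling delays frozen section one for one. The 4 to 22 minutes rest on assumed durations. Transfer and queue time inside the cCeLL reading time acts the other way by an unknown amount, so the net direction is not determined.

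Confidence is high that the clocks are not comparable, and lower on the size of the shift. The consequence is confined to a descriptive secondary endpoint and to the reading time carried into secondary endpoint 3. Agreement, sensitivity, specificity and the sample size are untouched. It should be corrected because the change is cheap and speed is part of the device's case.

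**What to change.** 1. Start both clocks at resection.
2. Define the end of cCeLL imaging as the last image, and state that reading does not overlap it.
3. Name these events in Section 6.6 and record three further time points per sample: start of cCeLL handling, release to pathology, and cCeLL read opened.
4. Report frozen-section time from resection twice: raw, and with the interval from start of handling to release removed. State that the adjusted figure assumes the handling delayed frozen section one for one. It may over-correct if part of that interval was a hold that the device did not cause, which is why both figures are needed.
5. Report cCeLL time from resection to read closed twice: with and without the interval from scan end to read opened. Label that interval as study logistics if reads are deferred.
6. Use read opened to read closed as the reading time in secondary endpoint 3.

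Cost: up to about 3 × 358 = 1,074 extra time entries, one redefined descriptive endpoint, and a reported time difference that may be less favourable to cCeLL. The sample size, the primary analysis and patient care do not change.
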